- l. Subjects who agree to participate in the photographic portion of the study will have photographs of warts taken before each treatment by the study team. If there are no warts remaining, the same areas will be photographed and repeated at the Follow-up Visits on Study Day 84 (−0/+8 days) (EOT) and Study Day 147 (±7 days) (EOS) regardless of whether warts are present. These images may be used on handouts in future trials, for training purposes, or future marketing materials. Photographs will be de-identified to those outside the research team and stored in a HIPAA compliant manner. Efforts will be made to ensure that no photographs with identifiable features are obtained.
- m. Application of study drug and surgical tape must be conducted by a study team member who is not considered, or has not acted as, the Blinded Assessor for the subject throughout the subject's participation. Surgical tape should only be removed at the designated removal time, when the treatment site is washed and study drug removed. Surgical tape and study drug may be gently removed from individual warts before the designated removal time in the event of significant blistering, significant pain, or treatment-emergent AEs. The surgical tape and study drug should not be removed from the remaining unproblematic warts until the designated removal time is reached. Removal of the surgical tape should be aided by soap and water, which will also help to prevent unroofing the blisters. Subjects who remove study drug before the assigned time frame will be considered a protocol deviation unless early removal is due to protocol defined criteria. Early removal is defined as removal of study drug outside of the following windows: ±1-hour window for the 2-hour duration of skin exposure group; ±2-hour window for the 6-hour duration of skin exposure group, and ±6-hour window for the 24-hour duration of skin exposure group.

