- n. In both Part A and Part B, an in-person follow-up ERT assessment will be conducted at each treatment visit (1-4) before study drug application and at Follow-up Visits on Study Day 84 (−0/+8 days) (EOT), Study Day 112 (±7 days), and Study Day 147 (±7 days) (EOS). In addition, for Part A Treatment Period 1 only, an in-person follow-up ERT assessment will be conducted at 48 hours (±8 hours). Follow-up telephone assessments for ERT will be conducted at 24 hours (±6 hours), 7 days (±24 hours), and 14 days (±24 hours) after each treatment visit (1-4) in which study drug is applied. Assessments will be recorded by the research team member on the ERT form. All ERT safety assessments must be conducted by a qualified member of the research team. ERT assessments and telephone calls must be conducted by a study team member who is not considered, or has not acted as, the Blinded Assessor for the subject throughout the subject's participation.
- o. Subjects will be provided with take-home instructions describing how to remove the surgical tape, the possible LSR's, and what to expect over the next 24 hours to several months. A 24-hour emergency number will also be provided. The next visit date/calls and time will be indicated on the form. An LSR Guide for subjects will be reviewed at the clinic with the subject by the research team, with copies provided for home use in the required post-treatment ERT follow-up telephone calls. Both take home instructions and LSR Guide will be provided and reviewed after each treatment to ensure understanding and confirm the education materials are available.

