An ERT assessment will be conducted at each treatment visit (1-4; in-person before treatment or via follow-up telephone calls) at 24 hours (± 6 hours), 7 days (± 24 hours), and 14 days (± 24 hours) after each treatment visit (not “unscheduled” visits). Note that the ERT telephone calls at 24 hours (± 6 hours), 7 days (± 24 hours) and 14 days (± 24 hours) are not required if there was no treatment during that period. In Part A Treatment Period 1 only, subjects will return to the clinic for an in-person ERT assessment at 48 hours (± 8 hours) after Treatment Visit 1. The ERT includes questions related to removal of surgical tape and study drug (if applicable) and collects any new AEs, LSRs, and changes in concomitant medications since the last contact. The subject will be given an opportunity to ask questions and review any concerns. In the event that any post-treatment LSR presents a safety concern (including but not limited to severe blistering, ulceration, edema, or pain) an “Unscheduled” clinic visit must be scheduled, and the subject assessed accordingly. In addition, if any post-treatment AEs present a safety concern, the subject may be brought in for an unscheduled visit. The ERT assessments will be recorded by a research team member on the ERT form. The ERT visits may not be conducted by a person designated as a Blinded Assessor. Phone calls conducted outside of the required study visits or required ERT assessments should be documented in the subject’s source note but are not required to be entered in the electronic data capture (EDC) system.

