ERT assessments, wart count, and wart location will be conducted before treatment application at all Treatment Visits 1 to 4, as well as at the EOT Visit on Study Day 84 (0/+8 days) and at the Follow-up Visits on Study Day 112 (± 7 days) and Study Day 147 (± 7 days). Wart measurement will be conducted before treatment application at Treatment Visit 1, as well as at the EOT Visit on Study Day 84 (-0/+8 days) and at the Follow-up Visits on Study Day 112 (± 7 days) and Study Day 147 (± 7 days). Subjects who clear all warts before the Study Day 84 (EOT) Visit will still be required to return for each of the scheduled in-person treatment visits, as well as the Study Day 84 (EOT) Visit, the Study Day 112 follow-up visit, and the Study Day 147 (EOS) Visit. A Provider Treatment Questionnaire will be completed at the Study Day 84 (EOT) Visit by a clinician who applied treatment to the subject during the course of the study. All subjects will continue in the study for two additional Follow-up Visits on Study Day 112 and Study Day 147 (EOS).

All treatment visits will include a wart count, performed before treatment (if applicable) and before ERT assessment. No treatment will be required if the wart is considered clear. Genital warts that develop in areas that are unable to be treated, (e.g., close to a

mucous membrane) and other wart types (e.g., common warts) will not be evaluated, documented, or considered in the analysis.

Wart counts will be conducted at the Screening Visit, Treatment Visit 1, Treatment Visit 2, Treatment Visit 3, Treatment Visit 4, End of Treatment Visit, and Follow-up Visit by a trained member of the study team. Other than the screening visit and Day 1, wart counts will also be conducted by a member of the research team that has been identified and trained as a Blinded Assessor. The Blinded Assessor may be utilized for a subject's initial screening, enrollment and treatment Visit 1 activities, however, may not perform any other study related activities other than wart counts at subsequent visits (e.g., follow-up phone calls or unscheduled visits) for the same subject. The Blinded Assessor is not required to be the same person for each assessment.

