It can sometimes be challenging to determine if a wart is completely clear after treatment due to ongoing LSRs. At any visit in which the Investigator is unable to evaluate or treat some warts due to ongoing LSRs, an "Unscheduled" visit should be documented. The timing of the next visit will be determined by the resolution of the LSR. The research team should be in contact with the patient until LSRs are resolved sufficiently and a treatment visit can be scheduled within 21 \pm 4 days when possible. Specific instructions on how to conduct the initial wart count and measure wart diameter will be provided during Investigator training.

At designated sites, photography will be offered to volunteer subjects who consent to participate. Photography will take place at the clinical site at each treatment and follow-up study visit through Study Day 147 (\pm 7 days; EOS). If there are no warts remaining, the same areas will be photographed and repeated at the Study Day 84 (0/+8 days) EOT Visit and Study Day 147 (\pm 7 days) EOS visit, regardless of whether warts are present. The images may be used on handouts in future trials, for training purposes, or future marketing materials. They will not be used for any portion of the efficacy or safety data. Photographs will be de-identified to those outside the research team and stored in a Health Insurance Portability and Accountability Act (HIPAA) compliant manner. Efforts will be made to ensure that no photographs with identifiable features are obtained.

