9.3.1.1 Day 1 (Treatment Visit 1)

Screening and Treatment Visit 1 may occur on the same day. If the Screening Visit and Treatment Visit 1 are not on the same day, repeat the following procedures:

- Confirm that subject still meets enrollment criteria (dermatologic exam; ability to attend study visits)
- Obtain relevant medical history since Screening Visit
- Obtain genital wart history (duration and previous treatments) since Screening Visit; if treated, confirm date of last treatment
- Clinical assessments
 - Measure vital signs (temperature, heart rate) before application of study drug
- Wart assessments (wart count, location by anatomical location, wart diameter measurement) conducted before application of study drug
 - Conducted by a study team member who is not considered, or has not acted as, the Blinded Assessor for the subject throughout the subject's participation
- Dermatologic exam
- Photography before application of study drug
 - Subjects who previously agreed to participate in the photographic portion of the study will have photographs of warts taken by the study team
- Record any prior medications (including non-prescription and herbal [complementary medicine] products) since the Screening Visit
 - Record any antimicrobial, antiviral, steroidal, or topical drugs received within 30 days before Day 1.
 - Record any non-pharmacologic treatments (e.g., ice packs, heat packs, warm soaks, etc.) administered in the 72 hours before application of study drug.

The additional procedures listed below are also completed as part of Treatment Visit 1:

- Laboratory assessments
 - Perform urine pregnancy test on female subjects of child-bearing potential (i.e., females who are capable of menstruating) before study drug application
- ERT assessment conducted before study drug application
 - All ERT safety assessments must be conducted and recorded on ERT by a qualified member of the research team; ERT assessments must be conducted by a study team member who is not considered, or has not acted as, the Blinded Assessor for the subject throughout the subject's participation
 - Warts that develop in areas that are unable to be treated, (e.g., close to a mucous membrane) will not be evaluated, documented, or considered in the analysis
- Study drug application
 - Apply study drug
 - Apply surgical tape
- Assess, identify, and record any AEs
- Record any concomitant medications

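### The protocol is inconsistent on what the Blinded Assessor may do at Treatment Visit 1, so in Part B the rater of the primary endpoint may know the randomised wash-off duration

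*Protocol*

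**What the plan says.** The permission appears twice in the protocol, in the synopsis (efficacy procedures) and in Section 6.1.3.2. The Blinded Assessor may be used for "initial screening, enrollment and treatment Visit 1 activities, however, may not perform any other study related activities other than wart counts" at later visits. The restriction to wart counts thus begins after Visit 1, and no Visit 1 task is carved out.

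Other places restrict the same person:

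- Table 1 footnote m: "Application of study drug and surgical tape must be conducted by a study team member who is not considered, or has not acted as", and then "the Blinded Assessor for the subject throughout" the subject's time in the study. It makes no exception for Visit 1.
- Table 1 footnote n, which covers Visits 1 to 4: "ERT assessments and telephone calls must be conducted by a study team member who is not considered, or has not acted as, the Blinded Assessor".
- Section 6.1.3.2 itself: "The ERT visits may not be conducted by a person designated as a Blinded Assessor".
- Section 9.3.1.1, on the Visit 1 wart assessments repeated when screening was on another day: "Conducted by a study team member who is not considered, or has not acted as, the Blinded Assessor for the subject".

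The clearance endpoint uses the blinded assessment only (SAP 8.4.2), with clearance defined as a count of zero on the blinded wart count form (SAP 9.1).

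**The concern.** Visit 1 is when drug and tape go on and the subject is told how to remove them, with a removal time of 2, 6 or 24 hours. In Part B the two durations are randomised (Section 6.1.2). A person who works at that visit under the broad permission can learn the subject's duration and then rate that subject's clearance at every later visit.

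Part B's primary objective is to pick the regimen with the better balance of benefit and risk (Section 5.0). A rater who expects more from the longer exposure could settle doubtful residual skin differently by regimen. The protocol accepts that such doubt arises: "It can sometimes be challenging to determine if a wart is completely clear after treatment due to ongoing LSRs". Sites may also staff Visit 1 under different rules, depending on which section they follow.

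**Working it through.** The documents give no figure to reproduce, so the check sets the texts side by side, task by task, for Treatment Visit 1.

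| Visit 1 task | Synopsis and 6.1.3.2 permission | Specific rule elsewhere | Result |
|---|---|---|---|
| Apply drug and tape | Allowed, no exception | Barred by footnote m. Section 9.3.1.1 is silent; Section 9.3.2.1 states the bar for Visits 2 to 4 | Conflict, and the visit-level section does not resolve it |
| ERT | Allowed, no exception | Barred by footnote n, Section 6.1.3.2 and Section 9.3.1.1 | Conflict |
| Wart assessments | Allowed, no exception | Barred by Section 9.3.1.1 when repeated | Conflict |
| Enrolment | Allowed | No bar | Open to the assessor |
| Removal instructions | Allowed | No bar in Section 9.3.1.1 or footnote o | Open to the assessor |

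The last two rows matter most. A site that obeys every bar can still let the assessor give the removal instructions, and so learn the duration. No text requires the assessor to be unaware of it. Section 8.6 describes the blind in terms of the study drug, not the exposure time.

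**Who could be affected.** Section 6.1.2 allocates 90 Part B subjects 3:3:2:2. That gives 90 × 3/10 = 27 in each VP-102 arm and 90 × 2/10 = 18 in each placebo arm. The between-regimen reading of VP-102 therefore concerns at most 27 + 27 = 54 Part B subjects. Only those whose later rater learned the duration are exposed. The documents do not say how many that would be, and the assessor need not be the same person each time.

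**Which comparisons it reaches.** Let d be the net share of Regimen 1 subjects whose call changes because the rater knows the duration. For illustration, assume d is the same on VP-102 and placebo, and that calls in Regimen 2 do not change. Half of the pooled placebo subjects come from each regimen (18 of 36).

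- VP-102 Regimen 1 minus Placebo Regimen 1 (tested): d − d = 0
- VP-102 Regimen 1 minus VP-102 Regimen 2 (observational): d − 0 = d
- VP-102 Regimen 1 minus pooled placebo (SAP Section 8 sensitivity analysis): d − d/2 = d/2
- Pooled VP-102 minus pooled placebo (SAP Section 8): d/2 − d/2 = 0

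Pooling in Part A keeps these halves, since each selected regimen adds five VP-102 subjects and one placebo subject. The documents give no basis for a value of d.

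**The case against.** The strongest reply is that the texts can be read together, as a general permission with specific exclusions. On that reading, one person who applies and tapes at Visit 1 and later rates the subject breaches footnote m. That is a deviation, not something the plan allows. This has force, but it does not settle the matter: the permission states no exception, Section 9.3.1.1 drops the application bar that Section 9.3.2.1 carries, and removal instructions are covered by no exclusion.

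The second reply is that duration masking was never promised. Subjects know their own removal time and could mention it at any count. In Part A the groups enrol in sequence (Section 6.1.1), so duration is apparent anyway. This stands for Part A. In Part B the duration is individually randomised, and the rater can largely be kept from it at little cost.

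The third reply is that the affected comparison is not tested. Section 12.3 tests VP-102 against placebo within each regimen and treats comparisons across regimens as observational. SAP 8.6 calls all comparisons exploratory, and the choice of regimen also weighs safety. All of this stands and limits the weight of the point. It does not remove it, because an untested comparison is read from its point estimates, and rater bias enters those directly.

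The remark about difficulty in judging clearance also has limits. It is qualified by the word sometimes and concerns ongoing local skin reactions, so it does not describe every Day 84 count.

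**Conclusion.** The inconsistency is real, and it leaves a route by which the rater of the primary endpoint can know the Part B duration. The exposure is confined to the between-regimen reading and, in diluted form, to the sensitivity analyses of each VP-102 regimen against pooled placebo. The size of any bias cannot be derived from the documents. It depends on how often a later rater learned the duration and on how far that shifts doubtful calls differently in the two regimens.

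Four stronger conclusions might be inferred, and the documents do not support them:

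- That the assessor is unblinded to VP-102 versus placebo. Each duration has its own placebo arm, so knowing the duration says nothing about assignment within it.
- That all 90 Part B subjects are rated by someone who knows their duration. Only a subject whose rater worked at that subject's Visit 1, or was told, is exposed.
- That the problem disappears where footnotes m and n are followed. Enrolment and removal instructions lie outside both.
- That the Table 1 wart count row adds a further conflict by assigning the screening and Visit 1 counts to the Blinded Assessor. The row has plain marks at those two visits and bracketed marks later, and footnote j starts the assessor's counts after Day 1. The label most plausibly refers to the bracketed marks.

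This should be corrected because the remedy is cheap and protects the blinded rating of the primary endpoint.

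**What to change.** In the synopsis and Section 6.1.3.2, replace the permission with text to this effect: the Blinded Assessor may take part in screening and other activities before randomisation only; at every visit, including Treatment Visit 1, this person may not apply study drug or tape, perform ERT or give removal instructions; and in Part B this person must not be told the assigned removal time.

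In Section 9.3.1.1, add to the drug and tape bullets the bar that Section 9.3.2.1 already states, and keep the existing bar on the Visit 1 wart assessments. Ask subjects not to mention their removal time to the assessor. This lowers the remaining risk but cannot remove it.

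The cost is protocol wording and a line in site training. The assessor is already separate from treating staff at Visits 2 to 4, so no extra staff are needed. The downside is slightly less flexibility in staffing Visit 1.

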6.1.3.3 Safety Procedures

Subjects will be provided with take home instructions describing what they might expect throughout the course of the study, as well as recommendations for wound care (if needed), when it is important to call their doctor, and instructions for who to contact in an emergency. In the event that any post-treatment LSR presents a safety concern (including but not limited to severe blistering, ulceration, edema, or pain), an “Unscheduled” clinic visit must be scheduled and the subject assessed accordingly. In addition, if any post-treatment AEs present a safety concern, the subject may be brought in for an unscheduled visit.

An LSR guide for subjects, with specific photographs representing the various skin reactions and examples of intensity, will be provided and reviewed in detail at the clinic with the subject by the research team. The LSR guide will be utilized for reference by the subject during the ERT follow-up telephone assessments with the research team member. The final determination of LSR parameters, including intensity, will be made by the research team member.

6.2 Number of Subjects

In Part A, 18 subjects will be enrolled into one of three duration of skin exposure groups (n=6 subjects/group). Each group will include a minimum of two subjects from each sex and will be randomized 5:1 (VP-102:placebo) within each group.

In Part B, 90 subjects will be enrolled, randomized to one of four treatment arms. Randomization will be stratified by sex so that neither gender exceeds ~60% of any treatment arm (e.g., placebo group for the 6-hour and 24-hour wash-off cannot have any one gender $\geq 60\%$).

6.3 Measures Taken to Minimize Bias

Bias is minimized by subject randomization and blinding (Section 6.5).

6.4 Expected Duration of Subject Participation

Study duration from Treatment Visit 1 through the final follow-up visit is approximately 147 days (21 weeks). The length of study participation is approximately

84 (–0/+8) days for the EOT assessment (primary endpoint) and Study Day 147 (± 7) days to complete the study, in addition to the screening visit of up to 14 days before study drug administration. The study will consist of up to four applications of study drug at intervals of 21 ± 4 days. All treatments will take place within a 75-day period. No treatment should be administered after Day 75 without the Sponsor's approval. Post-treatment Follow-up Visits on Study Day 84 (–0/+8 days) (EOT), Study Day 112 (± 7 days), and Study Day 147 (± 7 days) are included for subjects to evaluate the durability of treatment response over time.

6.5 Method of Treatment Assignment and Blinding

After informed consent has been obtained, subjects will be screened for study eligibility before randomization. Subjects will be assigned a subject number and randomized. In Part A, each group will include a minimum of two subjects from each sex randomized 5:1 (VP-102: or placebo). In Part B, randomization of the four treatment arms (VP-102 Regimen 1:VP-102 Regimen 2: Placebo Regimen 1:Placebo Regimen 2) will be 3:3:2:2. The study site's pharmacist (or pharmacist designee) will obtain the study drug assignment from the Interactive Response Technology (IRT). A subject is considered randomized when the randomization transaction is recorded in the IRT.

The Sponsor will remain blinded to study medication assignment until the study is completed and the database is locked, with the exception of cases in which unblinding is required due to a safety or tolerability issue. In the case of a medical emergency requiring the PI to know the identity of the study drug, the PI will follow the procedures outlined in [Section 8.6](#).

7.0 SELECTION, DISCONTINUATION, AND WITHDRAWAL OF SUBJECTS

The study will enroll and treat approximately 18 adult subjects in Part A and approximately 90 subjects in Part B presenting with EGW and a wart count of 2 to 30, inclusive. Eligibility to participate in the study will be determined by the Investigator on the basis of the inclusion and exclusion criteria.

